Table A-3: AEs related to Anaphylactic reaction and Anaphylactic shock (by PT) based on SMQs.....	47

LIST OF TABLES

	Page
Table 1. Schedule of Assessments.....	13
Table 2. Summary of Inferential Efficacy Analyses	37

LIST OF ABBREVIATIONS

AE	Adverse Event
AIS	Acute Ischemic Stroke
ANCOVA	Analysis of Covariance
CI	Confidence Interval
CRU	Clinical Research Unit (responsible for the Electronic Data Capture system)
CTA	Computerized Tomographic Angiography
CTP	Computerized Tomographic Perfusion
ASPECTS	Alberta Stroke Program Early Computerized Tomography Score
BI	Barthel Index
BNT	Boston Naming Test
DWI	Diffusion Weighted Imaging
ECG	Electrocardiogram
EMS	Emergency Medical Services
e-CRF	Electronic Case Report Form
FLAIR	Fluid Attenuated Inversion Recovery
ICH	Intracerebral Hemorrhage
ICA	Internal Carotid Artery
IDMC	Independent Data Monitoring Committee
IQR	interquartile range
ITT	Intent-to-Treat
MedDRA	Medical Dictionary for Regulatory Activities
MCA	Middle Cerebral Artery
MoCA	Montreal Cognitive Assessment
MRP	Magnetic Resonance Perfusion
mRS	Modified Rankin Scale
NCCT	Non-contrast Computed Tomography Scan
NIHSS	National Institutes of Health Stroke Scale
O-F	O'Brien-Fleming
PP	Per Protocol
SAE	Serious Adverse Event
SD	Standard Deviation
SNAP	Sunnybrook Hemispatial Neglect Procedure
SOC	System Organ Class
TEAE	Treatment-emergent Adverse Event
mTICI	Modified Thrombolysis in Cerebral Infarction scale
tPA	Tissue Plasminogen Activator

1.0 INTRODUCTION

This document provides the details of statistical analyses planned for Protocol No. NA-1-007. In addition, it discusses the statistical issues relevant to these analyses (e.g., sample data to be used and missing data).

1.1 Background

NA-1 is a synthetic, cell-permeant eicosapeptide (20 amino acids) that perturbs protein-protein interactions on the cytosolic surface of the cell membrane mediated by post-synaptic density 95 protein (PSD-95)^[1], an abundant protein localized in post-synaptic densities of central nervous system neurons. It may provide significant benefit for the treatment of acute cerebral ischemia if administered to stroke patients who present to medical attention before infarction is complete. The rapid progression of irreversible brain injury in most acute strokes implies a short window of clinical efficacy of any treatment, including NA-1. The ability to identify patients with salvageable brain using the criteria used in the ESCAPE trial^[2] provides an opportunity to target patients who may have the greatest benefit from neuroprotection, and to enhance further the impact of reperfusion therapies.^[3] Our preclinical and clinical data support this notion.

The rationale for this study is as follows:

1. There is no convincing evidence from randomized controlled trials that neuroprotection can be of clinical benefit to patients with AIS. There is however, extensive preclinical evidence that neuroprotection is of greatest benefit for improving functional outcome in studies employing experimental animal stroke models in which stroke is followed by reperfusion, as compared with stroke models in which arterial vessel occlusion is undertaken without reperfusion.
2. The neuroprotectant, NA-1, has been demonstrated to be highly effective in reducing stroke size and improving the functional outcome of experimental animals subjected to acute stroke, including rats and primates. NA-1 is more effective in reducing infarct size and improving functional outcome in models of ischemia-reperfusion, as compared with permanent arterial occlusion.^[4, 5]

3. NA-1 has an excellent safety profile in preclinical animal studies, a human Phase 1 trial, and a human Phase 2 study (the ENACT trial),^[6] Patients in the ENACT trial were also individuals who were being subjected to an endovascular procedure (intracranial aneurysm repair) and to treatment with NA-1 or placebo.
4. The ESCAPE and other recent trials of endovascular thrombectomy for AIS have demonstrated that modern acute endovascular therapy can rapidly recanalize blocked major arteries in patients with acute stroke arising from large artery occlusion with a low complication rate and high complete reperfusion rates.^[2, 7-9] This paradigm replicates the preclinical animal ischemia-reperfusion models in which neuroprotectants have the highest demonstrated efficacy.
5. NA-1 has shown promising results in reducing ischemic brain damage in humans having demographics similar to those of stroke patients.^[6]
6. There is a compelling need to develop neuroprotectants in order to increase the proportion of patients who may benefit from recanalization therapies. These agents could improve the outcomes of those who receive endovascular recanalization and make more patients into candidates for endovascular or pharmacological recanalization treatment.

1.2 Objectives

1.2.1 Primary Objectives

The primary objective is to determine the efficacy of the neuroprotectant, NA-1, in reducing global disability in subjects with major acute ischemic stroke (AIS) with a small established infarct core and with good collateral circulation who are selected for endovascular revascularization.

1.2.2 Secondary Objectives

The secondary objectives are to determine the efficacy of NA-1 in:

- Reducing functional dependence
- Improving neurological outcome
- Improving activities of daily living
- Reducing mortality rate

1.2.3 Tertiary Objectives

The tertiary objectives are to determine the efficacy of NA-1 in:

- Improving health-related quality of life.
- Decreasing infarct volume at follow-up imaging
- Improving cognitive function

1.2.4 Leading Safety Objectives

The leading safety objectives are to determine the effect of administering a dose of 2.6 mg/kg (up to a maximum dose of 270 mg) intravenous (IV) infusion of NA-1 to subjects with acute stroke who are selected for endovascular revascularization on the incidence of serious adverse events (SAEs) and 90-day mortality.

1.3 Study Design

This is a Phase 3 randomized, multicenter, blinded, placebo-controlled, parallel group, single-dose design. Per inclusion/exclusion criteria, subjects suffering an acute stroke who are selected for endovascular revascularization in accordance with local institutional practices and who present with a small established infarct core with good collateral circulation, will be given a single, 2.6 mg/kg (up to a maximum of 270 mg) intravenous dose of NA-1 or placebo. Ideally, dosing should begin within 30 minutes of randomization and within 60 minutes of the NCCT.

A total of 1120 subjects aged 18 years and older will be enrolled into the study. A patient who consents but is not randomized will be considered a screen failure. A subject is considered randomized the moment the randomization process is completed on-line. This is time “0” for the study. All subjects will be followed for 90 days (or until death if prior to 90 days). Subjects who are randomized but do not receive study drug will still be followed through the 90-day study period. The end of study is defined as the date that the last enrolled subject has completed their Day 90 visit.

The Schedule of Assessments is presented in [Table 1](#).

1.4 Sample Size Determination

Assuming a 52% overall responder rate for the placebo group, there will be 81.7% power to detect an 8.7% absolute effect difference between response rate (proportion of responders, with Day 90 mRS in the range 0 to 2) with NA-1 and placebo, at alpha level 0.05, 2-sided with a planned sample size of 1076 evaluable subjects, randomized 1:1, per group, accounting for a single interim analysis when 600 subject have reached their primary endpoint assessments, with O'Brien-Fleming alpha-spending function (EaST[®] V6.3) stopping boundary for overwhelming efficacy and a non-binding 1% conditional power futility stopping boundary. (See [Section 3.0](#) for further details on the interim analysis.) The sample size will be inflated approximately 4% to N= 560 per group to account for loss-to-follow-up and dropouts.

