11 STATISTICS

11.1 Sample Size Considerations

Assuming a 52% overall responder rate for the placebo group, there will be an approximately 80% power to detect an 8.7% absolute effect difference between response rate (proportion of responders, with Day 90 mRS in the range 0 to 2) with NA-1 and placebo, at alpha level 0.05, 2-sided with a planned sample size of 1076 evaluable subjects, randomized 1:1, per group, accounting for a single interim analysis when 600 subject have reached their primary endpoint assessments, with O'Brien-Fleming alpha-spending function (EaST® V6.3) stopping boundary for overwhelming efficacy and a non-binding 1% conditional power futility stopping boundary. The sample size will be inflated approximately 4% to N= 560 per group to account for loss-to-follow-up and drop-outs.

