3.0 INTERIM EFFICACY ANALYSES

An efficacy interim analysis after approximately 600 subjects complete the Day 90 follow-up (~56% information) will be conducted by the unblinded statistician in the independent Statistical Group (ISG) using the alpha spending function method^[11] with O'Brien and Fleming^[12] type stopping boundary for efficacy and a non-binding conditional power boundary (based on the observed trend at the interim analysis) for futility. Overwhelming efficacy at the interim analysis would occur if the test statistic crosses the O-F superiority boundary. For an interim analysis conducted at exactly 55.8% information, the superiority critical p-value for stopping (boundary value) would be 0.003 and that at the end of the study (primary analysis) would be 0.024, 1-sided. Conversely if the conditional power estimate based on the observed trend at the interim is <1% the trial may be deemed to be futile, contingent on consideration of other safety and efficacy factors (i.e., the futility boundary is nonbinding).

The IDMC may recommend stopping for futility at the interim analysis if the test statistic crosses the O-F or conditional power boundary. However, notwithstanding the O-F superiority critical p-value of 0.003 for stopping (boundary value) at the interim analysis of the primary efficacy outcome, the IDMC will be instructed that it should not recommend to stop the trial for overwhelming efficacy unless otherwise instructed by the Steering Committee at the Open Session of the IDMC meeting. The IDMC Charter will provide further details on the rationale for, and how, these recommendations will be communicated.

To prevent operational bias all interim results on safety and efficacy will be reported only to the IDMC, keeping the sponsor, project team, investigators and subject blind to results by treatment assignment during the study. Firewalls will be in place at the Statistical Group preparing all interim reports to protect and sequester all interim results on safety and efficacy

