5.0 MISSING DATA AND DATA TRANSFORMATION

5.1 Missing Data

Every effort will be made to keep missing data, particularly the Day 90 outcome assessments, to a minimum. However, some missing data may be inevitable due to, for example, loss to follow-up. This was kept to a minimum of 1.3% in the ESCAPE trial.^[2] Deceased subjects will be assigned scores of 6 on the mRS, 42 on the NIHSS, 0 on the Barthel Index and be counted as non-responders. For the primary analysis for regulatory submission, we will assume that subjects who are missing the primary endpoint data will be considered non-responders. If more than 5% of subject randomized are missing the primary endpoint, two sensitivity analyses will be employed to examine alternatives to this extreme single-value imputation: (1) multiple imputation of the ordinal mRS score which will then be converted to the corresponding binary score; and (2) if, as expected, $\leq 5\%$ of the mRS data are missing, a completers' analysis.

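### SAP 1.4 and the protocol print 1076 per group although it is the total, and the SAP's 81.7% power is for evaluable subjects rather than for 1120 analysed with missing scored as non-response

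*SAP*

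**What the plan says.** **Size and power.** SAP 1.4: "Assuming a 52% overall responder rate for the placebo group, there will be 81.7% power to detect an 8.7% absolute effect difference", "at alpha level 0.05, 2-sided with a planned sample size of 1076 evaluable subjects, randomized 1:1, per group". Protocol 11.1 uses the same inputs, and the protocol synopsis repeats them. Protocol 11.1 says "there will be an approximately 80% power to detect an 8.7% absolute effect difference between response rate", also "with a planned sample size of 1076 evaluable subjects, randomized 1:1, per group".

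**Inflation.** SAP 1.4 then states: "The sample size will be inflated approximately 4% to N= 560 per group to account for loss-to-follow-up and dropouts". Protocol 11.1 says the same. Protocol section 6 and SAP 1.3 put total enrolment at 1120.

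**Analysis.** The primary analysis is on the ITT population, meaning everyone randomized (Protocol 11.2.1, SAP 2.1). For missing Day 90 mRS, SAP 5.1 says "we will assume that subjects who are missing the primary endpoint data will be considered non-responders". Protocol 11.3 and 11.8 and SAP 7.1.3 agree. Both documents cite 1.3% missing in the predecessor trial.

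Neither sample-size section mentions the non-responder rule, or says whether the 52% already allows for it.

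**The concern.** The two per-group figures cannot both be right: a size of 1076 per group cannot be inflated to 560 per group.

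The other difficulty is what the inflation is for. Adding subjects for dropout restores power when lost subjects leave the analysis and those remaining show the full effect. Here nobody leaves. A lost subject stays in the denominator and counts as a failure, so both response rates, and the difference between them, shrink by the proportion missing. The extra subjects restore the number of observed outcomes but not the size of the effect. The stated power of a pivotal trial should be the power of its stated primary analysis, and a reader should be able to recover the sample size without guessing which label is wrong.

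**Working it through.** **Inputs.** p1 = 0.52, p2 = 0.52 + 0.087 = 0.607, two-sided alpha 0.05, 1076 evaluable, 560 per group after inflation, interim at 600 (SAP 1.4); conditional-power futility limit of 1% under the observed trend (SAP 3.0).

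**Step 1: is 1076 the total?**
- 2 × 560 = 1120, and 1120/1076 = 1.041, which is the stated inflation of about 4%.
- 600/1076 = 55.8%, the fraction used in SAP 3.0. With 1076 per group it would be 600/2152 = 27.9%.
- The stated power agrees with 538 per group (step 2) and not with 1076 per group (step 3).

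**Step 2: reproduce the stated power with 538 per group.** For a fixed design,

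power = Φ{[δ − 1.96·√(2p̄(1−p̄)/n)] / √([p1(1−p1) + p2(1−p2)]/n)}.

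With δ = 0.087, p̄ = 0.5635 and n = 538, the two standard errors are 0.03024 and 0.03012. Power = Φ[(0.0870 − 0.0593)/0.03012] = Φ(0.92) = 82.1%.

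The two-look design used O'Brien-Fleming-type spending at one-sided 0.025, with the interim at 600/1076 and a bivariate normal for the two statistics. It gives 82.1% (unpooled variance) or 81.8% (pooled), and 81.6% or 81.3% if the futility stop is obeyed. The SAP's 81.7% lies within this range, so it is the power for 538 evaluable subjects per group.

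**Step 3: the literal reading.** With n = 1076 the standard errors are 0.02138 and 0.02130. Power = Φ[(0.0870 − 0.0419)/0.02130] = Φ(2.12) = about 98%.

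**Step 4: the planned analysis.** Keep n = 560 per group and multiply both rates by (1 − m), where m is the proportion missing in each arm. At m = 0.04:
- rates 0.52 × 0.96 = 0.4992 and 0.607 × 0.96 = 0.5827; difference 0.0835
- standard errors 0.02978 and 0.02968
- power = Φ[(0.0835 − 0.0584)/0.02968] = Φ(0.85) = 80.2%

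The table covers the fixed design and the two-look design. The lower end of each range is pooled variance with the futility stop obeyed.

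| Missing | Rates after scoring | Difference (points) | Power, 560 per group |
|---|---|---|---|
| 0% | 52.0% v 60.7% | 8.70 | 82.8–83.6% |
| 1.3% | 51.3% v 59.9% | 8.59 | 81.7–82.5% |
| 2% | 51.0% v 59.5% | 8.53 | 81.1–81.9% |
| 4% | 49.9% v 58.3% | 8.35 | 79.3–80.2% |
| 5% | 49.4% v 57.7% | 8.27 | 78.4–79.3% |
| 10% | 46.8% v 54.6% | 7.83 | 73.7–74.6% |

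At 4% missing, 80% power needs 558 per group without the futility stop, so the planned 560 suffices. Recovering 81.7% would take about 583 per group.

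**The case against.** The labelling error has no defence. Against the power point there is a fair case.

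- **It is conditional.** The documents call 52% an overall responder rate and do not say among whom. If 52% and 60.7% already count missing subjects as failures, the 0% row applies and 81.7% is conservative. This stands, and the plan should say which is meant.
- **The 4% is an allowance.** The only observed loss rate cited is 1.3%, at which power is at or above 81.7%. This stands too.
- **The protocol's figure survives.** Approximately 80% describes the planned analysis at 4% missing. Only the SAP's more precise figure is affected.
- **The calculation is unadjusted.** The primary test is a Wald test from a covariate-adjusted logistic regression, so tenths of a point mean little. The comparison is still like for like, because the same unadjusted calculation reproduces the SAP's own number.

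A reader might go further and infer that the interim information and boundary are also wrong, because 600/1120 = 53.6% and the one-sided boundary there is 0.0022. The documents do not support that. SAP 3.0 ties the look to subjects with observed outcomes: "An efficacy interim analysis after approximately 600 subjects complete the Day 90 follow-up (~56% information"; SAP 1.4 also says "accounting for a single interim analysis when 600 subject have reached their primary endpoint assessments". Observed over evaluable is 600/1076 = 55.8%. On the ITT scale, 600 completers with a matching 4% missing are 600/0.96 = 625, and 625/1120 is again 55.8%. SAP 3.0 gives 0.003 and 0.024 for exactly 55.8% information. They recompute as 0.0027 and 0.0241, so they are correct to rounding, and the spending function resets them if the fraction differs.

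**Conclusion.** The sample-size statement is wrong as written on one count and incomplete on another.

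1. Without any assumption: 1076 is the total, 538 per group, and the per-group label is an error in three places.
2. Conditionally: the SAP's 81.7% is the power with losses removed, not the power of the ITT analysis with missing scored as failure. At the plan's own 4% loss, power is about 80% (79.3% to 80.2%), which is 1.5 to 2.4 points below 81.7%. This assumes that the planning rates apply to observed subjects and that loss is equal in the two arms. At 1.3% missing it is about 82%, and the shortfall disappears.

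It does not follow that the trial is underpowered or should enrol more. The protocol's target of approximately 80% is met at 4% missing, and power drops to about 74% only at 10% missing. The information fraction and interim boundaries are not in question.

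**What to change.** - In the protocol synopsis, Protocol 11.1 and SAP 1.4, write 1076 evaluable subjects in total (538 per group).
- In SAP 1.4, state whether 52% and 60.7% are rates among observed subjects or are already net of non-responder scoring.
- If they are rates among observed subjects, restate the SAP power as about 80% for 1120 ITT subjects with 4% missing scored as non-responders, in line with the protocol. Give a short range over missing rates, for example 1.3%, 4% and 10%.

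The cost is wording and one figure, and the SAP's headline power becomes slightly less favourable. Enrolment, the analysis, the information fraction and the interim boundaries stay as they are.

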1.5 Randomization

Treatments (placebo vs. NA-1) will be assigned 1:1 by application of a stratified minimization algorithm administered through a secure web-based, real-time interaction with the site and the central server. The time of randomization on the central server will be considered baseline (i.e., time zero) for the study. Study drug is intended to be infused within 30 minutes post-randomization and within 60 minutes of the NCCT. Although each vial of NA-1 or placebo will have a unique ID number that will be linked to the randomization code generated by the minimization algorithm, the vials will appear to be identical to those dispensing them and to the subjects. Thus, individuals at the sites will be blinded to the treatment assignments.

In order to balance the treatment assignment among subjects receiving different combinations of adjunct thrombolytic and thrombectomy therapies, randomization will be stratified by (1) intravenous thrombolysis with alteplase (yes/no) and by (2) a subject's initial thrombectomy approach (stent retriever vs. thrombus aspiration device). Planned initial use of any other endovascular device type or intra-arterial medications will constitute an exclusion criterion. Similarly, if intravenous thrombolysis is planned for the subject, use of any intravenous thrombolytic other than alteplase is an exclusion criterion. Thus, there will be 4 randomization strata:

- a. Alteplase+stent retriever
- b. Alteplase+thrombus aspiration device

- c. Stent retriever without Alteplase
- d. Thrombus aspiration device without Alteplase

All subjects, investigators, their clinical staff, the clinical coordinating center, the data management group, and the sponsor staff and delegates will be blinded to the randomization codes. The local laboratories will also be blinded.

Table 1. Schedule of Assessments

++	Baseline	Post- EVT (~2 h)	Day 1 (24 ± 12 h from random- ization)	Day 2 (48 ± 8 h from randomization)	Day 5 or discharge (±1 d)	Day 30 (±5 d)	Day 90 (±14 d)
Informed consent	X						
Attempt at regained capacity informed consent*			X	X	X	X	X
History and examination	X						
Weight	X*				X (Actual)		
Vital Signs (BP, HR, Temp) ★★	X	X	X	X	X		
Randomization/ Study drug administration	X						
Mortality					X	X	X
NIHSS	X	X	X	X	X	X	X
mRS			X¶		X	X	X
Barthel Index	X					X	X
BNT15, SNAP, MoCA¶¶							X
EQ-5D-5L						X	X
NCCT head	X						
CTA (Circle of Willis)	X						
Endovascular Procedure	X						
MR head			X**				
CBC, electrolytes, INR, aPTT, serum creatinine and serum glucose	X‡		X				
Pregnancy test	X‡‡						
Immunogenicity sample‡‡‡			X			X	
Pharmacokinetic samples‡‡‡‡	X						
ECG	X‡		X				
AE assessment	Collected to Day 30 visit						
SAE assessment	Collected to Day 90 visit						
Prior medications	X§§						
Concomitant medications	Collected to Day 30 visit						

* If the original process involved anyone other than the subject (and if required), site staff will make ongoing efforts until (1) regained capacity consent is obtained from subject, (2) death, or (3) completion of the Day 90 assessment.

★★ Vital signs (BP, HR only) should be recorded immediately before and after completion of the study drug infusion, temperature will be taken at baseline per standard of care. ¶ Historical (pre-stroke) score

¶¶ Assessments will be conducted only if the tool/scale is available in local language.

* At baseline estimated or actual weight

** Day 1 MR head may be supplanted by an NCCT head if MR is unavailable or contraindicated.

‡ ECG testing and Blood should be drawn at baseline, but results are not required prior to randomization. For ECG, if treating physician deems that pre-treatment ECG impedes access to timely care, ECG must be completed within 6 hours of randomization.

‡‡ If the subject is female and is of childbearing potential a pregnancy test (urine or serum point-of-care pregnancy test) must be completed and the result must be negative; this is the only mandatory laboratory test prior to randomization

‡‡‡ Immunogenicity samples will be taken from a subset of up to 250 subjects at Canadian and US sites.

‡‡‡‡ PK samples will be taken from up to 100 subjects at a subset of Canadian and US sites. Samples will be taken at pre-dose and at 10, 20, 30, 60 and 120 min after the start of drug administration.

§§ Prior medications should be documented but their documentation not required prior to randomization.

d = days; h = hours

